## Objectives

In our R21 preliminary work, we demonstrated the feasibility and acceptability of ROSE, a computerized intervention for perinatal women with recent IPV who seek mental health treatment. In our pilot work, there were high ratings of satisfaction for ROSE. 100% completed the computerized intervention; 93% participated in the booster and 92% in the 4-month follow up assessment. Further, participants in the ROSE condition demonstrated a significantly larger change in frequency of IPV from baseline to follow-up (4 months after intake) than participants in the control condition ( $p < 0.007$ ).

The goal of this proposed study is to build upon these promising preliminary findings by testing whether ROSE reduces the frequency of IPV in a larger sample of perinatal women seeking mental health treatment, compare the effects of ROSE to an attention, time, and information matched control condition in two real-life clinical settings, examine the effects of the intervention for a more extended period of time, and include a cost estimate of ROSE. To achieve this, we propose a two-group, randomized controlled trial in which 186 perinatal women seeking mental health treatment are assigned to either (a) a computer-delivered, single-session brief intervention plus one interventionist-led phone booster; (ROSE); or (b) a computer-delivered control + one interventionist-led phone booster condition. Computer-delivered follow-up assessments will occur at 6-weeks, 3 months, 6 months, and 12 months after the baseline assessment. More specifically, we propose the following Specific Aims:

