**Site Differences:** In the preliminary analyses, participants from the two sites will be compared on all demographic and background information. We will also check for site effects with each specific hypothesis by including site as a fixed effect factor in the analysis. Site main effects and, as appropriate, interactions of site with relevant factors will be included. If site differences (and the interactions) are non-significant, this factor will be removed. Including site as a fixed effect and assuming an equal distribution of participants between sites and by treatment within each site will not change the overall sample size needed. However, the study may lack power to detect a site-by-treatment interaction unless the difference is large. Powering the study to detect the expected treatment effect separately by site is not feasible and would elevate the site-effect to a higher aim as opposed to being a check on the analysis[77].

**Aim 1:** For hypothesis 1 (primary outcome), the outcome (frequency of IPV) will be analyzed under a clustered count regression framework (Poisson or Negative Binomial) with frequency as outcome, and time (6-weeks, 3-, 6- and 12 months,), group (ROSE, control) and time-by-group interaction, with the

baseline (BL) IPV frequency as the primary covariate. A generalized linear mixed models (GLIMMIX) approach will be adopted by means of a random subject intercept to account for the clustering within each participant. Changes over time within each group will be estimated post-hoc by sliced effects derived from the regression model with adjustment for multiple comparisons. In additional analysis, reduction in proportion of participants experiencing a binary outcome of  $IPV \geq 1$  days within the 90-day period will be analyzed using a clustered logistic regression with a dichotomous outcome, again with BL IPV frequency as a covariate.

**Aim 2:** Similar analyses will be conducted for the secondary outcomes of positive affect and well-being and for perceived emotional support (Aim 2a and 2b). For cost estimation (Aim 2c) see below.

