**Aim 3:** The mediation tests will examine the ability of the proposed mediators, empowerment and self-efficacy, to account for all or part of the possible main effect of treatment on outcome. The mediators will be assessed at the end of treatment, and outcome will be taken from subsequent time points. We will use the product of coefficients test[78] to determine the magnitude and significance of mediated effects. This method multiplies the parameter estimate for the intervention predicting the mediator with the parameter estimate for the mediator predicting the outcome ( $\alpha\beta$ ). We will estimate the standard error and 95% confidence interval of  $\alpha\beta$  by bootstrapping, a re-sampling method that performs well when the assumption of normality may not hold.

**Missing Data:** Missing data will be handled by a weighted complete data analysis, using only complete cases after weighting the cases with the inverse probability of being missing. The probability is calculated as a function of the variables that are simultaneously associated with the outcome of interest and the event of being missing itself.

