**Power:** We calculated the sample size using mean, standard deviation, and within-subject correlation estimates for IPV frequency from our R21 study. IPV frequency was measured by the CAS Total score. In our pilot data, we observed participants in ROSE demonstrated a significantly larger change in frequency of IPV than the control condition. The observed between-group effect size for change in IPV frequency at follow up was moderate to large: Cohen's  $d$  of 0.59 and 0.68 with and without adjustment for baseline score. Therefore, a more conservative effect size of  $d = 0.4$  was selected for sample size estimation. With four follow up IPV assessments, a within-subject correlation of 0.62, and a standard deviation of 20, 74 participants per group are needed to detect an effect size of  $d = 0.4$  for the overall intervention vs. control group difference with 80% power at the 5% significance level. A minimum effect size of  $d = 0.4$  will be detectable for the secondary outcomes of positive affect and well-being and perceived emotional support. The secondary outcome measures are reported as T-scores based on a normative mean of 50 and standard deviation of 10. With 74 patients per group and assuming an observed SD of 10, a 4-point difference in positive affect and well-being or perceived emotional support will be detectable. Moderate effect sizes (Cohen's  $f$  for multiple regression = 0.39) for mediated effects of the intervention ( $\alpha$  and  $\beta$ ) will be detectable with 80% power and 74 patients per group[79]. For all the outcomes, our proposed sample of 186 should be adequate for detecting small to moderate effect sizes. Even assuming the worst-case scenario of up to 20% drop-out in both the ROSE and control groups, we plan to recruit 93 participants per arm.

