## 6. WITHDRAWAL OF SUBJECTS

Study staff will be trained on understanding the various potential risks of participation in this study, as explained above, in the section "Risks and Benefits." As explained in this section, various procedures will be put into place to mitigate these potential risks. However, if when discussing the safety of a subject's participation in the study, study staff decides that stopping a subject's participation is necessary for safety reasons, then study staff will withdraw the subject from the study. As explained in the "Risks and Benefits" section, we anticipate that potential circumstances in which this might need to occur include breaching of confidentiality, coercion of participants, participant discomfort, the occurrence of study-related partner violence, and/or social or legal consequences related to study participation.

If participants voluntarily withdraw from the research, study staff will keep the data that has already been collected, and will use this data in the study analysis procedures. If a participant is physically present when she decides to withdraw from the study, she will be checked in with by research staff, be given any relevant informational handouts if it is safe for her to receive and take with her, and be given any relevant referrals.

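### The complete-case rule, on its usual meaning, discards follow-up scores that the withdrawal section says will be used and that the Aim 1 model can use; the cost is precision

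*Combined protocol and SAP*

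**What the plan says.** Section 6 (Withdrawal of Subjects) deals with women who leave voluntarily: "study staff will keep the data that has already been collected, and will use this data in the study analysis procedures".

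Section 4 (Data Management), Missing Data paragraph, sets a weighted complete-data analysis, "using only complete cases after weighting the cases". It does not define a case. It describes one probability of missingness per case, not one per visit, and no analysis of all available data is planned beside it.

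Section 4, Aim 1 paragraph, models CAS frequency on "time (6-weeks, 3-, 6- and 12 months,), group (ROSE, control) and time-by-group interaction", with baseline frequency as covariate. It does so "by means of a random subject intercept to account for the clustering within each participant". Aim 2 is to be analysed similarly.

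Section 4, Power paragraph: "With four follow up IPV assessments, a within-subject correlation of 0.62, and a standard deviation of 20, 74 participants per group are needed" for d = 0.4 with 80% power at the 5% level. Recruitment is 93 per arm to allow for 20% drop-out.

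The only retention figures are from the pilot, in Section 1 (Objectives): "93% participated in the booster and 92% in the 4-month follow up assessment".

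**The concern.** Take a woman who gives CAS scores at 6 weeks, 3 months and 6 months and then withdraws. Section 6 says her data are used. Under the usual meaning of a complete case, the Missing Data paragraph removes all three scores from the primary model. A woman who stays in the trial but misses one assessment loses her other three scores in the same way. Her case follows from the Missing Data paragraph alone, since Section 6 covers voluntary withdrawal only.

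A random-intercept model needs no such restriction, because it takes whatever visits each woman has. The plan would therefore give up information on its primary outcome that it has already collected. Two analysts could also follow the text and build different primary data sets.

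**Working it through.** **Inputs from the Power paragraph.** Four follow-ups, within-subject correlation 0.62, SD 20, d = 0.4 (8 points), 93 recruited per arm. A two-sided 5% test is assumed, because sidedness is not stated.

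**The plan's own figure.** For the mean of four equally correlated measures, the variance factor is (1 + 3 × 0.62)/4 = 0.715. The normal approximation gives n = 2 × ((1.960 + 0.842)/0.4)² × 0.715 = 98.1 × 0.715 = 70.1, so 71 per group. A t-based version gives 72. The stated 74 is close, with about 82% power. Then 74/0.80 = 92.5, so 93 per arm, as stated. The sample size is not in dispute.

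**Drop-out only.** Assume the 20% is spread evenly over the four visits, so 5% of women leave before each one. Per arm, 93 × 0.80 = 74.4 women are complete. Another 93 × 0.15 = 14 women gave one, two or three visits, and 93 × 0.05 × (1 + 2 + 3) = 28 collected visits are discarded. On the unadjusted variance, power is about 82% with complete cases and 87% with all visits.

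**Missed visits only.** The documents give no per-visit miss rate. The rates below are assumptions, with misses independent across visits; 8% is borrowed from the pilot's 92% at one follow-up.

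- Share of women complete at miss rate m: (1 − m)⁴.
- Information from a woman with k visits: 1/(B + R/k), where B is the between-woman and R the residual variance.
- Adjusted for baseline at correlation 0.62: B = 0.62 × 0.38 × 400 = 94.2 and R = 0.38 × 400 = 152.
- Unadjusted: B = 0.62 × 400 = 248 and R = 152.
- Standard error = √(2/(93 × mean information per woman)); power = Φ(8/SE − 1.96).

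At 8%, adjusted, mean information per randomised woman is 0.00734 with all visits and 0.00542 with complete cases. The ratio is 1.35, and √1.35 = 1.16.

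| Miss rate | Complete per arm | SE ratio, adjusted (complete cases / all visits) | Power, unadjusted: complete cases vs all visits | Power, adjusted: complete cases vs all visits |
|---|---|---|---|---|
| 2% | 93 × 0.922 = 86 | 1.04 | 87% vs 90% | over 99% for both |
| 5% | 93 × 0.815 = 76 | 1.10 | 83% vs 89% | 99% vs over 99% |
| 8% | 93 × 0.716 = 67 | 1.16 | 78% vs 89% | 98% vs over 99% |

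The number complete falls to 80% of those recruited at m = 1 − 0.80^(1/4) = 5.4%.

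**If misses cluster.** If the same women miss repeatedly, the share complete at 8% per visit lies between 0.92⁴ = 72% and 92%, which is 67 to 86 women per arm. At the upper end the women who miss have no follow-up data to discard, and the loss disappears.

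**Bias.** A simulation used 600 trials per setting and 93 women per arm. Drop-out was monotone and twice as likely after a high last CAS score, with correct weights on baseline and arm. At 81%, 74% and 66% completers, the SD of the estimated difference was 1.91, 1.89 and 2.10 with weighted complete cases, against 1.78, 1.69 and 1.86 with all visits: 7% to 13% larger. Bias was negligible when drop-out worked the same way in both arms.

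All of these figures use a normal approximation, whereas Aim 1 specifies a Poisson or negative binomial model.

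**The case against.** The strongest reply is that the plan never defines a complete case. Mixed models are normally fitted to person-visit rows. If a case is a row, every collected visit stays in and the conflict disappears. Section 6 also promises use in the analysis procedures generally, and a leaver's data could still enter the baseline tables or the weighting model. So a reader might infer that the two rules cannot both be followed, and the documents do not go that far. What stands is that the row reading is nowhere stated, that weighting is described per case with a single missingness event, and that on the ordinary reading the primary outcome scores of these women are lost.

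Three further inferences are tempting.

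- *The 20% allowance will be exceeded by missed visits alone.* This needs independent misses above about 5.4% per visit. The pilot's 92% is retention at a single follow-up and may already include drop-outs, so it is not a missed-visit rate.
- *The trial becomes underpowered.* The 78% at 8% misses uses the unadjusted variance. Aim 1 adjusts for baseline, and at correlation 0.62 that keeps power near 98%.
- *The result will be biased because abused women leave.* The background finding, that currently victimised women were more than twice as likely to leave, concerns mental health treatment in a chart review, not research follow-up. Nor does the Missing Data paragraph limit the weights to baseline variables, and the simulation showed negligible bias.

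It is also fair to say that inverse-probability-weighted complete-case analysis is a recognised method. The objection here is that it wastes collected data and sits badly with Section 6, not that it is invalid in principle.

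**Conclusion.** The point holds as a conflict in the text with a cost in precision. On the usual meaning of a complete case, the Missing Data paragraph discards follow-up CAS scores that Section 6 says will be used and that the Aim 1 model could use. The cost is a standard error about 4% to 16% larger for independent miss rates of 2% to 8%, and less if misses cluster. Those rates and the independence are assumptions. The consequence for power depends on the variance used: a fall from about 89% to 78% at 8% misses without baseline adjustment, and about 98% or more either way with it. Bias, an exceeded drop-out allowance and an inadequate sample size are not shown. The change is worth making because it recovers information at almost no cost and fixes the primary data set in advance.

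**What to change.** In the Missing Data paragraph of Section 4, replace the complete-case rule for Aims 1 and 2 with wording such as: *The mixed model is fitted to all available follow-up assessments of every randomised woman, including visits collected before voluntary withdrawal.*

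Keep inverse-probability weighting as a sensitivity analysis. Apply weights to each observed visit, based on the probability of being observed at that visit given baseline and earlier visits. The current text weights by the inverse of the probability of being missing. That is a separate point: correcting it would not restore the discarded visits.

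Add a cross-reference in Section 6 saying that this is how retained data enter the analysis.

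The cost is a few sentences, with no new data and no change of model. The small downside is that the primary analysis then relies on data being missing at random given the observed visits and the model covariates, which is why the weighted analysis should stay as a check.
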